Risk Evaluation and Education for Alzheimer's Disease – the Study of Communicating Amyloid Neuroimaging (the REVEAL-SCAN Study)

Statistical Analysis Plan

April 29, 2021

National Institutes of Health/National Institute on Aging: RF1 AG047866

ClinicalTrials.gov Number: NCT02959489

Aim 1: To determine whether disclosure of elevated brain amyloid will bias ADCS-Preclinical Alzheimer Cognitive Composite (ADCS-PACC) test results and subjective memory.

Study Subjects: Those who are Amyloid positive (A+)

Outcome: ADCS-PACC, measured twice (6 wks., 6 mos.) (primary), and subjective memory measures Metamemory in Adulthood Questionnaire and Memory Functioning Questionnaire (secondary), measured twice (6 wks., 6 mos.)

Primary Hypothesis 1.1: At 6 months after disclosure, ADCS-PACC scores will be lower among A+D+ participants than A+D- participants.

Primary Analysis 1.1: For this aim we focus on one outcome, ADCS-PACC, and thus use an alpha level of 0.05 to determine statistical significance. First, we will obtain descriptive statistics for those who are in the D+ and D- groups among A+ subjects. Then, we will compare ADCS-PACC scores between D+ and D- groups among A+ subjects using a two-sided test of means. Next, we will compare D+ and D- groups on potential confounders. We will initially consider confounders due to the Covid-19 pandemic (as described below) and then consider other confounders (including age, education, premorbid function, experiences of discrimination). If any are significantly different between the two groups ($p < 0.05$), despite randomization, we will conduct regression analysis adjusting for those confounders that are different. Analyses will be repeated measures (6 wks. and 6 mos.) adjusting for baseline measure at time of randomization. We will focus on 6 month differences, but also check for time-averaged differences between D+ and D- groups. Check ADCS-PACC for normality. If normal, linear regression analysis for repeated measures can be used, specifically a mixed-effects model with repeated measures (MMRM). If not normal, we will use an appropriate transformation to make the distribution more normal. We will also conduct an Intention-to-Treat (ITT) analysis, which will incorporate information from those who drop out over the 6 months, assuming missing at random. This analysis will have better control of type 1 error and power. We will model time as a categorical measure, and the primary outcome will be the estimated difference (contrast) between the two groups (D+ and D-) at 6 months and secondarily the time-averaged difference. We will also apply a model with 3 repeated measures (baseline, 6 wks., 6 months) without adjustment for baseline ADCS-PACC to examine the full trend over time, but this will be a secondary analysis.

Analysis 1.1 if we do not reach planned sample size: Our plan for this study is to recruit 270 subjects who would be randomized equally to D+ and D- groups. With 10% loss, we expect 120 subjects in each group with about 50% being A+ due to enrichment of *APOE* e4+ participants. Thus, there would be ~60 people in each of the four groups: A+D+, A+D-, A-D+, A-D-. For Aim 1, we powered the study to detect a difference between the A+D+ and A+D- groups. With 60 subjects in each of these two groups, we have 80% power to detect a difference of 1.15 ADCS-PACC points. After pursuing this plan for several years we found that the expected 50% split between A+ and A- participants was too optimistic and in fact we found that the proportion of A+ subjects enrolled in the study was hovering between 25% and 30%, thereby reducing the numbers available for evaluation of Aim 1, the primary research question for the study. In June, 2018, we applied for a supplement to this research project to aid us in attaining needed sample size for Aim 1. We revised our estimated sample size needed for Aim 1 to be 50 in each group (A+D+, A+D-), determining that we could detect a moderate meaningful difference of 1.2451. If we are not able to attain the sample size that we expect (~50 in each group), we will conduct an analysis of the existing sample. If the result is significant, we then had more power than we thought we might; that is, the difference between the two groups was greater than 1.2451. If the difference between the two groups is not significant, we will examine the confidence interval for the difference to obtain a range of estimates of possible differences, given our sample size.

Outliers: Components of the ADCS-PACC and the overall score will be examined for outliers. We will exclude values that are more than 2 standard deviations from expected mean values (based on the literature). In addition, we will consult visit notes and TOMM scores to see if anything unusual might be a factor in the outliers.

Missing PACC data: Some participants may be missing or have invalid components of the PACC. If missing more than 1 of the PACC components, the participant will be excluded from analysis. If missing 1 or fewer of the PACC components, we will conduct multiple imputation analyses to fill in missing values. Multiple imputation datasets will be derived and analyses will combine results over the imputed datasets, following standard procedures for imputation. For a sensitivity analysis, we will also conduct an analysis excluding these individuals.

Adjusting for Covid-19: The Covid-19 virus impacted the tail end of our study; as a result some visits did not occur when planned. For example, the 6 month visits ranged from 3 months to 14 months. Thus, our primary analysis will adjust for the actual time of the visit. In addition, we will include a dichotomous variable indicating whether the visit occurred after March 15, 2020 or not, since the existence of the Covid-19 virus, a widespread, acute psychological trauma, may have affected the study participants' responses. We will examine the impact of the Covid-19 virus prior to considering other confounders that might impact the results. As a benchmark of comparison, we will also conduct an analysis using the categorical times of the planned visits. Likewise, we will also conduct an analysis that excludes observations after March 15, 2020.

Secondary Hypothesis 1.2: A+D+ participants will have higher scores on scales of subjective memory complaints than A+D- participants.

Secondary Analysis 1.2: Two instruments have measured subjective memory: (1) Metamemory in the Adulthood Questionnaire (108 questions) with two subscores and (2) Memory Functioning Questionnaire (64 questions) with 5 subscores. Thus, these two questionnaires result in 7 different scores. Results from all 7 are summarized in Lineweaver et al paper (2014). Lineweaver et al used two-way MANOVA on all 7 and then proceeded to two-way ANOVA for each of the 7. We plan to conduct this same analytical plan.

Exploratory Hypothesis 1.3: Differences in PACC scores between disclosed and non-disclosed will be larger for African American participants than all other race groups combined.

Exploratory Analysis 1.3: The analysis will be the same as the primary analysis, but now conducted only in the African Americans in the study. If the hypothesis is true, we expect a larger difference, but the study is not powered for this subgroup analysis. To formally test whether African Americans have a greater response, we will perform analyses of the full group of A+ individuals, adding an interaction term to the model for race * disclosure group.

Aim 2: To determine whether disclosure of elevated brain amyloid will cause psychological distress.

Study Subjects: All Study Participants and the subgroup of A+ subjects

Outcomes: IES (Impact of Event Score), measured twice (6 wks., 6 mos.), and INI-AD, measured twice (6 wks., 6 mos.)

Hypothesis 2.1: At 6 weeks after disclosure, A+D+ participants will have greater IES scores and INI-AD scores than A-D+ or D- participants.

Analysis 2.1: Analysis will generally use the same methods as Aim 1. For this Aim, IES is the primary outcome for which we will use an alpha level of 0.05. INI-AD is a secondary outcome. Our main focus for this aim is contrasting scores between the A+D+ and A-D+ groups. We will also contrast the A+D+ and the D- groups (as long as the A+D- and A-D- exhibit similar outcomes). As in Aim 1, we will obtain

descriptive statistics between the two groups (A+D- and A-D+ for the first contrast and then A+D- vs the D- group). We will also evaluate the confounding effect of Covid-19 as described in Aim 1 and subsequently other potential confounders for these contrasts and incorporate if needed in further regression analyses. Note that there is no IES at baseline. So there is no adjustment for a baseline measure. The same holds true for INI-AD. One major difference here is that the IES and INI-AD are not normally distributed and cannot be transformed to become so. Thus, we will use generalized linear models fit with generalized estimating equations using a log link and a gamma distribution. If needed, we will add a value of 1 to all scores to shift the distribution away from zero and use a log transform on the data. We will focus on the differences at 6 weeks, but also evaluate the time-averaged differences.

Exploratory Hypothesis 2.2: Comparison of outcomes at 6 weeks and 6 months after disclosure will show African Americans to be equally vulnerable to psychological distress as measured by IES and INI-AD after amyloid imaging compared to all other racial and ethnic groups.

Exploratory Analysis 2.2: Analyses will be the same as described above for IES and INI-AD applied to the subgroup of African Americans. To formally test whether effects are the same, we will add an interaction term to the model for race to evaluate whether African Americans experience similar distress as those in the study who are not African American.

Aim 3: To explore how amyloid imaging disclosure will impact preventative health behaviors, advance planning for health (e.g. long-term care insurance decisions) and well-being (e.g. stigma, quality of life and relationships).

Study Subjects: All Study Participants, contrasting D+ and D- participants. Additionally, we will compare the A+D+ subjects to the A-D+ subjects.

Outcomes: We will focus on outcomes at 6 months of follow up after disclosure.

Measures: We have several categories of behavior to examine.

- 1) Preventive Health Behaviors: diet, vitamin intake, physical exercise and mental exercise, medication changes
- 2) Advance Planning: long-term care insurance decisions, other insurance decisions, completion of advance directives
- 3) Well-being: stigma, quality of life and relationships, sharing of information

Aim 3 Hypotheses:

Preventive Health Behaviors:

D+ individuals will show equivalent probability of undertaking preventative health behavior changes as D- individuals.

A+D+ individuals will show a higher probability of undertaking more preventative health behavior changes than A-D+ individuals.

Advance Planning:

Advance planning will occur with a similarly low frequency in D+ and D- individuals.

Advance planning will occur more frequently for A+D+ individuals than A-D+ individuals.

Well-Being:

D+ individuals will report more sharing of information than D- individuals.

Sharing of information will not differ between A+D+ and A-D+ individuals.

D+ individuals will report more stigma compared to D- individuals. This effect will be modified by amyloid status. A+D+ individuals will report more worries about stigma than A-D+ individuals.

D+ individuals will report similar QOL compared to D- individuals. This effect will be modified by amyloid status. A+D+ individuals will report lower levels of quality of life than A-D+ individuals

Aim 3 Analyses: While we will examine each measure individually, our primary analysis will focus on aggregate summary measures for: 1) any preventative health behavior changes made over 6 months since disclosure that the participant reports, and 2) any advanced planning measures taken over the 6 months since disclosure. Separate bivariate analyses will be conducted for each of these summary measures. For 1) and 2), we will contrast the D+ and D- groups using chi-square statistics. We will also contrast the summary measures in the disclosed group by those with elevated and not elevated brain amyloid. We will conduct multivariable logistic regression analyses to control for any variables that appear to be confounders. We will use follow-up analyses to elucidate factors driving significant main effects.

For 3) Well-being, we will examine group differences in each stigma, quality of life and relationships, sharing of information at 6 months post disclosure. We will examine mean differences between groups on two measures of stigma (AD concern since learning risk/amyloid & Social Impact Scale) and conduct outlier analyses to identify potential predictors of extreme responses. We will use ordinal logistic regression to examine differences in quality of life as measured by an estimate of the impact of risk estimate/PET. To examine relationships and result sharing, we will use two-stage models to examine (a) decisions to share with others and (b) levels of satisfaction with this sharing. Analyses of decisions to share information will include a participant's sharing of each a risk estimate and an amyloid test result. Binary outcomes will be examined using unadjusted proportions and adjusted odds ratios. Analyses of satisfaction will include rank ordered levels of satisfaction with decision to share, of sharing a risk estimate, and of sharing an amyloid result. We will contrast groups defined by disclosure and amyloid status.

Adjusted models will control for measured factors unbalanced across study groups and baseline values will be assessed as predictors of Aim 3 outcomes. All Aim 3 analyses will be conducted in the full group and also in the subgroup of disclosed study participants. Prior to analysis we will check that all model assumptions are adequately met. If not, we will adjust the analysis plan accordingly. Since these are exploratory analyses, we will use an alpha level of 0.05 to assess statistical significance. We will report estimates and their respective 95% confidence intervals.

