Eyetracking data and questionnaire data from the 6-month follow-up visit related to stereotype threat and the digit span task will be analyzed by the University of Southern California (USC) team. All data will be de-identified before being sent to USC for analysis. Each site will upload their de-identified, raw pupillometry data (labeled with subject ID#) to the BU secure Web data repository and from there it will be sent to USC.

Data Analysis

The analytical strategy will focus on comparing A+D+ and A+D- groups on the ADCS-PACC score at 6 months to better identify if non-disclosure itself had an effect on ADCS-PACC performance. Although the primary comparison is not based on the fully randomized groups, it is a comparison of randomized groups in the pre-specified subgroup of A+ subjects, thus controlling for type 1 error. The power calculation is based on the comparison within the subgroup of A+ subjects, so type 2 error is also controlled. Our primary analysis will use a mixed-effects model repeated measures (MMRM)⁵⁷ approach to evaluate the three repeated measures over time. This Intention-to-Treat (ITT) analysis will incorporate information from those who drop out over the 6 months, assuming missing at random, and have better control of type 1 error and power. We will model time as a categorical measure, and the primary outcome will be the estimated difference (contrast) between the two groups at 6 months. As randomization may not be fully successful in balancing confounding factors between the groups (subgroups of the randomized groups), the analysis will also adjust for potentially confounding measures such as sex, age and *APOE* genotype. We will also include the baseline measure of the ADCS-PACC score in one regression model (using the two repeated measures at 6 weeks and 6 months) to allow for differences in cognitive functioning at baseline. We will also consider models that examine change from baseline, with and without adjustment for the baseline measure.

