Analyses of IES as the main secondary outcome and of other measures, will be conducted in a similar fashion. While our main focus for the IES will be upon the contrast between the A+D+ and A-D+ groups, we will also contrast the A+D+ and the D- groups (as long as the A+D- and A-D- exhibit similar outcomes). The D- group may experience increased distress waiting for the disclosure of their imaging, which could reduce our power to explore comparisons between A+D+ and D- groups, although we did not see this occurring in our prior REVEAL studies when participants in the non-disclosure arms were waiting for their genotype data at the end of the study. It will also be of interest to compare the difference between A+D- and A-D- groups, because this comparison would reveal any differences in cognition due to the amyloid burden

itself among participants who do not learn their amyloid status at the fourth visit. We do not expect to find any difference here in only 6 months of follow-up. For Exploratory Aims 1.2 and 2.3, we will examine regression models or MMRM models with interaction terms for race and group to evaluate whether the differences at 6 months between the groups (e.g. A+D+ vs A+D-) are similar for AAs and non-AAs. Point estimates will be considered in addition to confidence intervals and p-values.

For the 6-month follow-up visit digit-span task, we will examine whether working memory performance and pupil dilation responses differ when under high than low threat differentially depending on both disclosure status and amyloid levels.

For the 6-month visit digit-span task, we will examine whether working memory performance and pupil dilation responses differ when under high than low threat differentially depending on both disclosure status and amyloid levels.

Power Calculation

Our objective is to achieve 80% power to detect a difference of moderate effect size (0.4-0.6 SD units) on the primary outcome of ADCS-PACC mean score between the A+D- and A+D+ groups at 6 months.

Assuming a PACC standard deviation of 2.2⁴⁴, 50 individuals per group would provide 80% power to detect a difference of 1.25 PACC units (0.52 SD units) between A+D- and A+D+ at 6 months.

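### SAP Primary Analysis 1.1 selects covariates by a between-arm p<0.05 test that the protocol does not use, and the SAP codes visit time in the primary model in two different ways

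*SAP*

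**What the plan says.** **Covariates.** SAP Primary Analysis 1.1 starts with pandemic-related confounders ("We will initially consider confounders due to the Covid-19 pandemic (as described below") and will "then consider other confounders (including age, education, premorbid function, experiences of discrimination"). Those that differ between D+ and D- at p<0.05 are adjusted for: "despite randomization, we will conduct regression analysis adjusting for those confounders that are different". Baseline PACC is in the repeated-measures model whatever the screen shows. Protocol section VI, Data Analysis, also gives possible imbalance as its reason for adjusting, but applies no test: "the analysis will also adjust for potentially confounding measures such as sex, age and" APOE genotype. Both lists are open. The SAP's does not name sex or APOE, and age becomes conditional.

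**Visit time.** Primary Analysis 1.1 states: "We will model time as a categorical measure, and the primary outcome will be the estimated difference (contrast) between the two groups", taken at 6 months, with the time-averaged difference secondary. The SAP paragraph on adjusting for Covid-19 reports 6-month visits held anywhere from 3 to 14 months. It says the primary analysis adjusts for actual visit time, and it makes the analysis by categorical planned times a benchmark. That paragraph also includes, without condition, an indicator for visits after 15 March 2020.

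**ITT.** The protocol describes its primary MMRM as the ITT analysis: "This Intention-to-Treat (ITT) analysis will incorporate information from those who drop out over the 6 months". The SAP says: "We will also conduct an Intention-to-Treat (ITT) analysis".

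**The concern.** A significance test of baseline balance between randomised arms tests a null hypothesis that is true by design. A covariate that passes has drifted by chance; that says nothing about whether it predicts PACC. The adjusted model is therefore unknown until the arms have been compared. A strongly prognostic covariate is left out unless it happens to be imbalanced, and a useless one may come in.

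The time coding bears on what the primary number means. The SAP does not say whether actual time is added to the categorical visits or replaces them. If it replaces them, the 6-month contrast is read off a fitted line; if it is added, the contrast belongs to the visit. When the disclosure effect changes between 6 weeks and 6 months and the visits are widely spread, these are different quantities under one name.

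**Working it through.** **Plan's own figure.** Inputs from the protocol's Power Calculation: 50 per group, SD 2.2, difference 1.25, 80% power; two-sided alpha 0.05 from the SAP. Power is 81.1% by the normal formula and 80.3% by the noncentral t. The detectable difference by the t method is 1.2449, against the SAP's 1.2451. The figure reproduces and is not in dispute. (1.25/2.2 = 0.568 SD, which is used below; the protocol prints 0.52.)

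**How often the screen fires by chance.** With the four named candidates, assumed independent: 1 - 0.95^4 = 18.5% of trials flag at least one.

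**What it lets through.** Largest unflagged imbalance at 50 per arm: t(0.975, 98) x sqrt(2/50) = 0.397 SD. The documents give no covariate strengths, so I assume a residual correlation with PACC of 0.1-0.2 and a baseline-to-follow-up correlation r of 0.5-0.8. Residual SD = 2.2 x sqrt(1 - r^2). Shift from one covariate just under the limit:
- 0.397 x 0.1 x 2.2 x sqrt(1 - 0.8^2) = 0.052 points
- 0.397 x 0.2 x 2.2 x sqrt(1 - 0.5^2) = 0.151 points

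That is 4% to 12% of 1.25. The standard error of the contrast is residual SD x sqrt(2/50) = 0.26 to 0.38, so the shift is 0.2 to 0.4 standard errors.

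**Type I error and power.** Simulation: ANCOVA standing in for the 6-month MMRM contrast, baseline PACC always included, three further covariates (one continuous, two binary with assumed prevalence 0.6), 50 per arm, 15,000 runs per setting.
- No effect: rejection 4.7-5.0% screened, 4.9% with a fixed list.
- 1.25 points, screened/fixed power at r = 0.5, 0.7, 0.8: 89.8/90.1, 97.7/97.5, 99.7/99.7 (correlation 0.1); 90.1/92.7, 97.8/98.4, 99.7/99.9 (correlation 0.2).
- 0.4 SD, the low end of the protocol's "difference of moderate effect size (0.4-0.6 SD units"): 62.2/62.2, 78.7/79.0, 90.8/91.0 (0.1); 62.7/66.7, 79.1/82.6, 91.1/93.5 (0.2).

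The gain from a fixed list runs from -0.2 to 4.0 power points.

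**Time coding.** Reading A: categorical visit, arm-by-visit, plus actual-minus-planned time as a covariate. Reading B: continuous actual time with arm-by-time, read at month 6. Assumptions: 50 per arm, SD 2.2, within-person correlation 0.5-0.8, complete data, 10-40% of 6-month visits spread over 3-14 months and the rest at 5.5-7 months, effect fixed per visit, 3,000 runs.

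| True effect, 6 weeks / 6 months | Reading A | Reading B |
|---|---|---|
| 1.25 / 0.625 | 0.63 | 0.71-0.80 |
| 0.625 / 1.25 | 1.25-1.26 | 1.09-1.17 |

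With the same effect at both visits, A and B estimate the same value. With no effect, both hold type I error (4.0-4.6%).

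**Sensitivity to the effect shape.** If the effect instead follows actual elapsed time, from 1.25 at 6 weeks to 0.625 at 6 months, the picture reverses: B gives 0.61-0.63 and A gives 0.46-0.58. The readings still differ, but which one is off depends on the shape assumed.

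**The case against.** **The screen is close to a matter of taste.** The protocol also justifies adjustment by imbalance, its list is open too, the precision at stake is small, and the 0.05-0.15 point shift is chance variation already covered by the standard error. The simulation used three generic covariates, not the SAP's four. All of this stands and limits the size of the point. It does not supply a reason for the screen, which still leaves the covariate set unfixed.

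**Visit time can be reconciled.** Adjusting for actual time fits a categorical model with a time covariate. That is a fair reading, but relegating the categorical-time analysis to a benchmark weighs against it, and the SAP does not settle the matter.

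**Stronger readings a reader might infer, which the documents do not support:**
- *The screen inflates type I error.* It does not, by the simulation above. Without baseline PACC in the model it made the test conservative.
- *The primary result could be a model with no arm-by-time term.* Such a model returns the time-averaged effect, (1.25 + 0.625)/2 = 0.94 in the first row of the table. Primary Analysis 1.1 makes the time-averaged difference secondary, so this reading is closed.
- *The Covid-19 indicator is subject to the p<0.05 screen.* Primary Analysis 1.1 defers to the later paragraph, which includes it outright.
- *The SAP contradicts itself on ITT.* The Covid-19 and missing-data paragraphs do not mention ITT. The difference is between the SAP and the protocol.
- *The two-sample test of means is the primary test.* Read together, the SAP points to the baseline-adjusted repeated-measures model.

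**Conclusion.** The point holds on two counts and should be fixed.

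First, the p<0.05 screen departs from the protocol and leaves the primary covariate set open, for no benefit. The cost is prespecification plus about 0 to 4 power points, under assumed residual correlations of 0.1-0.2 and baseline correlations of 0.5-0.8.

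Second, the SAP describes time in the primary model in two ways that can yield different 6-month estimates when the effect is not constant. A gap of roughly 0.1 to 0.2 points is plausible in the scenarios tried. That figure rests on an assumed share of displaced visits, complete data and an assumed effect shape, and its direction is not determined.

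Two lesser items need only wording: Primary Analysis 1.1 should say that the Covid-19 indicator is always included, and the SAP should say whether its primary MMRM is the ITT analysis, as in the protocol.

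**What to change.** - Drop the p<0.05 screen. Adjust for baseline PACC and a closed, prespecified list of baseline covariates (at least sex, age and APOE genotype), whatever the observed imbalance.
- Name one primary model: the MMRM of 6-week and 6-month PACC in all randomised A+ participants, analysed as randomised, with categorical visit and arm-by-visit terms defining the 6-month contrast, tested at two-sided 0.05. State that this is the ITT analysis. Note that it differs from the protocol's three-measure MMRM, which the SAP already makes secondary, and that participants with no follow-up PACC contribute no outcome to it.
- State in one place how actual-minus-planned visit time and the 15 March 2020 indicator enter. Both arise after randomisation, so adjusting for them is not protected by it; report the primary contrast with and without them.
- Label the test of means as preliminary. Label other time codings, other covariate sets and the analysis without observations after 15 March 2020 as sensitivity analyses.

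The cost is SAP rewording and a few model degrees of freedom. Sex, age, APOE genotype and visit dates are already collected.

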Relevance to future decision-making in both clinical trials and clinical practice. The major relevance of this work will be to the design of future clinical trials that use AD biomarkers such as amyloid as part of the inclusion criteria and the translation of their results into clinical practice. If we demonstrate substantive cognitive bias, the sample size of future trials may need to be increased, and sub-analyses of our data (not described in this proposal) could guide us to select tests or batteries of tests that are less vulnerable to stereotype bias. If we demonstrate that there are individuals who become anxious or severely distressed in response to learning their amyloid status, future trials may require processes for recognition and treatment of such symptoms. While our recruitment procedures will not result in a subject pool that is representative of clinical practice, these insights will also be relevant to guide clinicians in ordering and communicating results of amyloid imaging to cognitively normal individuals. Our study is not designed to formally measure costs or resource utilization, but will measure the degree to which subjects seek consultation and order additional diagnostic tests after obtaining amyloid imaging. This information will help researchers and clinicians begin to understand the downstream implications of amyloid imaging as it becomes increasingly utilized.

II. Specific Aims

We will enroll 370 cognitively normal individuals, aged 65-80, using *APOE* genotyping with oversampling of $\epsilon 4+$ individuals to enrich the enrollment sample such that roughly 30% of those scanned will be amyloid elevated (A+) and the remainder amyloid not elevated (A-). From this enriched sample, 370 participants (approximately 25% African American) will all receive their Alzheimer's Disease Dementia Risk Disclosure and be randomized (50/50) to either receive their amyloid scan results (Disclosure or D+) at the disclosure visit or not at the disclosure visit (D-). Those in the D- group will receive their amyloid scan results at an additional visit at the end of the study. The primary cognitive outcome will be the A4 Study's Preclinical Alzheimer Cognitive Composite and the primary outcome for psychological distress will be the Impact of Events Scale (IES). We plan the following analyses:

Specific Aim #1: To determine whether disclosure of elevated brain amyloid will bias ADCS-Preclinical Alzheimer Cognitive Composite (ADCS-PACC) test results.

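### The SAP drops primary-outcome PACC scores because of their size, which shrinks the A+D+ versus A+D- contrast if disclosure does lower PACC

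*SAP*

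**What the plan says.** The SAP's Outliers paragraph under Aim 1 sets the scope: "Components of the ADCS-PACC and the overall score will be examined for outliers". It then gives the rule: "We will exclude values that are more than 2 standard deviations from expected mean values (based on the literature". The next sentence reads: "In addition, we will consult visit notes and TOMM scores to see if anything unusual might be a factor in the outliers". The notes and effort test are therefore an extra look at the outliers, not a condition for dropping a score. The paragraph gives no mean, SD, source or visit for the rule. The only PACC SD in either document is the 2.2 in the protocol's Power Calculation.

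The primary model is described under Primary Analysis 1.1: "Analyses will be repeated measures (6 wks. and 6 mos.) adjusting for baseline measure at time of randomization". The other analyses named in the SAP for this outcome are an ITT analysis, a model with three repeated measures, an analysis by planned visit time, one without observations after 15 March 2020, and one without participants who have a missing PACC component. None is said to bring excluded outliers back. The protocol's Data Analysis section contains no outlier exclusion.

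**The concern.** The rule selects on the value of the outcome, measured after the intervention. The primary hypothesis is that A+D+ scores are lower than A+D- scores. If so, the A+D+ distribution has more of its mass beyond the lower cut and less beyond the upper cut, and trimming both arms at the same fixed limits pulls their means together. The repeated-measures model does not repair this. Its stated basis is data "which will incorporate information from those who drop out over the 6 months, assuming missing at random", whereas here a value is missing because of what it was.

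The size of the effect is a result the trial intends to use. The protocol's Background says: "If we demonstrate substantive cognitive bias, the sample size of future trials may need to be increased". If recruitment falls short and the result is not significant, the SAP says "we will examine the confidence interval for the difference to obtain a range of estimates of possible differences". An interval centred too close to zero would then rule out the true difference too often and falsely reassure trials that disclose amyloid status. Because the reference mean and SD are unstated, they could also be chosen after the data are seen.

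**Working it through.** **Inputs.** From the protocol's Power Calculation: SD 2.2, 50 per arm, difference 1.25. From the SAP: two-sided test, alpha 0.05. Assumed, because the documents do not give them: normal scores with equal SD, literature SD equal to 2.2 unless stated, the position of the A+D- mean relative to the literature mean, and the correlation r between visits.

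**1. The plan's own figure.** The protocol says "50 individuals per group would provide 80% power to detect a difference of 1.25 PACC units". SE = 2.2 × √(2/50) = 0.44, and 1.25/0.44 = 2.84. The two-sample t test then has 80.3% power, and 80.0% at the SAP's 1.2451. The figure reproduces.

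**2. Unadjusted contrast under the rule.** With the literature mean set to 0, the cuts lie at ±4.4. The mean of the retained values is μ + σ[φ(a) − φ(b)]/[Φ(b) − Φ(a)], where a = (−4.4 − μ)/σ and b = (4.4 − μ)/σ.

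- A+D-, μ = 0: a = −2, b = 2. 95.4% are retained, with mean 0 and SD 1.94.
- A+D+, μ = −1.25: a = −1.432, b = 2.568, φ(a) = 0.1431, φ(b) = 0.0147. 91.9% are retained, with mean −1.25 + 2.2 × 0.1284/0.9188 = −0.943 and SD 1.86.
- Difference 0.943, so shrinkage is 1 − 0.943/1.25 = 25%.
- Retained n is 47.7 and 45.9. SE = √(1.94²/47.7 + 1.86²/45.9) = 0.392, the noncentrality is 2.4, and power is 66%. Simulation of 20,000 trials gave 65.7%, against 80.0% with all values kept.

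| A+D- mean relative to literature mean | Deleted, D- | Deleted, D+ | Difference | Power |
|---|---|---|---|---|
| 0.5 SD below | 7.3% | 17.7% | 0.84 (−33%) | 58% |
| Equal | 4.6% | 8.1% | 0.94 (−25%) | 66% |
| 0.5 SD above | 7.3% | 4.6% | 0.95 (−24%) | 67% |

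The direction does not depend on the position of the mean. When a normal mean shifts, the truncated mean moves at the rate Var(truncated)/Var, which is below 1.

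**3. Baseline-adjusted two-visit model.** Scores at the three visits have common correlation r, and the effect is the same at both follow-up visits. The model has visit-specific arm and baseline terms with unstructured covariance. Post-baseline values beyond 2 SD are set to missing (2,000 replicates per scenario).

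| r | 6-month estimate with cohort 0.5 SD below / at / 0.5 SD above | Power, all values kept | Power under the rule |
|---|---|---|---|
| 0.7 | 0.99 / 1.08 / 1.09 (−20%, −13%, −13%) | 97–98% | 90–96% |
| 0.5 | 0.91 / 1.02 / 1.02 (−27%, −18%, −18%) | 89–91% | 73–81% |

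A single-visit ANCOVA agrees closely. At r = 0.85 it gives −12%, −8% and −8%.

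**4. Interval.** In these model scenarios, coverage of the true 1.25 falls from about 95% to 84–92%. The whole interval lies below 1.25 in 7–16% of trials instead of about 2.5%. With 40 per arm, coverage is 86–93% and the interval lies below in 6–14%.

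**5. Smaller effect.** For a true difference of 0.4 SD, with the cohort at or 0.5 SD below the literature mean, model power falls from 80% to 66–74% (r = 0.7) and from 61–63% to 46–54% (r = 0.5).

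**6. Uneven effect.** If the mean effect of 1.25 is carried by a quarter of A+D+ participants (cohort at the literature mean, unadjusted), the estimate falls to about 0.34. If half carry it, the estimate is about 0.80.

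**7. Unstated reference values.** With the literature mean within 0.5 SD of the cohort either way and the literature SD 0.8 to 1.2 times 2.2, unadjusted shrinkage runs from 11% to 48%. Model scenarios run within that range gave 6% to 41%.

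**8. No effect.** Rejection is 4.4–5.2% with the rule and 4.3–5.3% without it.

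**The case against.** The strongest reply is about size. The planned contrast is baseline-adjusted, so the fall from 80% to 66% belongs to the preliminary test of means. In the adjusted model at r = 0.7, power for 1.25 stays at 90% or more. If r were 0.85, the bias would be only 8–12%, with power above 99%. No correlation is given in the documents. This stands: at high r the harm is a biased estimate and poor coverage, not lost power.

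The interval argument also needs narrowing, because the SAP reads the interval that way only when the sample is short and the result is not significant. At 50 per arm, r = 0.7 and the cohort at the literature mean, the interval lies wholly below 1.25 in 8.8% of trials, but in 6.1% when the trial must also be non-significant (2.4% without the rule). At r = 0.85 that second figure is under 0.5%. At r = 0.5, and at 40 per arm with r = 0.7, nearly all the excess falls in non-significant trials, so the point survives where it matters most.

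The separate ITT analysis might be read as keeping every value. Its text mentions only dropouts, so this is an ambiguity and not a safeguard.

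The calculations model deletion of the overall score only. The SAP does not say whether an excluded component counts as invalid and is then imputed under its missing-data paragraph. A check of component-level deletion gave similar or larger attenuation, but the figures above are not exactly those of the rule as written.

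Finally, the direction was shown for normal shifts with equal variance, and the absence of bias under no effect requires equal distributions, not merely equal means.

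**Conclusion.** The concern holds, and the rule is wrong as written for a primary analysis. It removes valid scores by size against unstated reference values, and no planned analysis is stated to retain them. If disclosure lowers PACC, the primary contrast is pulled toward zero: by 13–27% in the baseline-adjusted model for r of 0.5 to 0.7, by 8–12% at r = 0.85, and by 24–33% unadjusted. These ranges assume normal scores, a true difference of 1.25, SD 2.2, and a literature mean within 0.5 SD of the cohort. The size depends on those assumptions; the direction was the same in every scenario run. Type I error is not inflated. The harm is a biased effect estimate, an interval that under-covers and, at moderate correlation or for smaller effects, a material loss of power.

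**What to change.** In the SAP's Outliers paragraph:

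- Remove the 2-SD exclusion from the primary analysis and keep every validly administered PACC score.
- Set a value to missing only for a documented administration or scoring error, judged blind to arm and amyloid status.
- Do not let TOMM performance alone justify exclusion, since it too is measured after disclosure.
- Move any 2-SD exclusion, winsorised or robust analysis to a sensitivity analysis, with the reference mean, SD and source stated in advance.
- Say whether the ITT analysis retains all values.
- Leave the planned multiple imputation for a single missing component as it is, and state that a component counts as invalid only for a documented error, not for its size.

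The cost is SAP wording. Residual variance will be larger than after exclusion (0.51 against 0.41–0.44 in squared SD units at r = 0.7), but that is the correct variance for the population studied.
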